6.3 Guidelines for Dose Modification

Grade 1 and 2 AEs require close follow-up but no change in treatment.

All grade 3 toxicities will be treated by the facility investigator as appropriate. Any grade 4 toxicity that, in the opinion of the investigator of the center, is directly related to the treatment of the study, will be treated with the permanent suspension of the study.

6.4 Trial Treatments

DRUG SUPPLY AND LABELLING

This study will use a drug already on the market and authorized for use in HIV-infected patients; The study drug is already taken regularly by these patients and will be distributed by the Pharmacy service of the Hospital Clínic. For clinical trials carried out in Spain, labelling in Spanish is mandatory in accordance with the regulations currently in force.

6.5 Trial duration

The approximate expected duration for the inclusion of patients is 12 months, and the duration of treatment and follow-up of the included patients will be extended by a maximum of 24 weeks

6.6 Termination and/or discontinuation criteria

The treatment will be **compulsorily** terminated during the study for any of the following reasons:

- Virologic failure, defined by two consecutive determinations of standard viral load >37 copies/mL separated by one week from each other.
- I express the patient's wish.
- Medical decision.
- Death.
- Pregnancy detection during the study.

Treatment **may** be terminated during the study for any of the following reasons:

- The medical investigator determines that a SAE is possibly or likely related to the study drug.
- Failure to administer, evaluate, or other study requirements.

If the confirmatory result is ≥ 37 copies/mL, a genotypic resistance detection study would be scheduled and the most appropriate attitude towards modifying their antiretroviral treatment would be discussed with the patient. In this case, unless he or she is against it, the patient would continue in the study.

All other virologic studies and immunological studies should be determined exclusively at baseline and 24 weeks (except if there is earlier virologic failure, in which case it would be performed at the time of confirmation of failure rather than at 24 weeks), and their determination should be deferred at the end of the study. To this end, plasma and peripheral blood mononuclear cell samples should be stored appropriately at -80°C until the planned determinations are made.

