1.9. Clinical Trial Phase: Phase IV

1.10. Objectives:**1.10.1. Main objective:**

The primary objective of this study is to determine the feasibility of maintaining virologic suppression on standard plasma viral load (limit of detection 37 copies/mL) of a once-daily dose reduction strategy of ATRIPLA® to three tablets per week in HIV-1-infected patients with sustained standard plasma viral load suppression for more than 2 years.

1.10.2. Secondary objectives:

- Virological study including: ultrasensitive viral load in plasma (limit of detection 1 copy/mL), and HIV-1 reservoir in peripheral blood mononuclear cells,
- Immunological study including: production of TREC, immune profile of activation (CD38 and HLA-DR) and senescence (CD57 and CD28) in CD4 and CD8 lineages, apoptosis (annexin V staining), and ratios of naïve T cells and effectors and memory cells (CCR7 and CD45RA).
- Pharmacokinetic study, including baseline plasma levels of efavirenz at the beginning and end of the study.
- Safety study, which includes: test on sleep quality, vitamin D levels, estimated glomerular filtration rate and plasma lipids at the beginning and end of the study, as well as general tolerability.

1.11. Design:

Open-label, randomized, Phase IV, prospective, pilot, single-center study.

1.12. Disease under study:

HIV infection (acquired immunodeficiency virus)

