1.13.2. Secondary

- Percentage of patients with virologic response viral load <1 copy/mL after 24 weeks.
- Change from baseline to 24 weeks in the viral reservoir of peripheral blood mononuclear cells
- Changes from baseline to 24 weeks in REBT production
- Changes in the immune profile of activation (CD38 and HLA-DR) and senescence (CD57 and CD28) in the CD4 and CD8 lineages, and in the proportions of naïve and effector and memory T cells (CCR7 and CD45RA).

- Changes in apoptosis levels in vitro by annexin V staining.
- Changes in plasma levels of efavirenz.
- Changes in sleep quality (Pittsburgh Sleep Quality Index), plasma levels of vitamin 25OH-D and lipids, and estimated glomerular filtration rate (CPK-EPI).
- Overall safety (reporting side effects, serious side effects, and discontinuation of treatment due to side effects)

1.14. Study population and total number of patients:

Adult patients with well-controlled chronic HIV infection and on treatment with ATRIPLA.® A total of 60 patients will be included.

1.15. Duration of treatment:

The approximate expected duration for the inclusion of patients is 12 months, and the duration of treatment and follow-up of the included patients will be extended by a maximum of 24 weeks.

1.16. Schedule and expected completion date:

The study is expected to begin, once the permits have been obtained, in March 2013. The recruitment period will be 48 weeks. The follow-up of the patients will last 24 weeks to start the study. The study is expected to be completed in October 2014.

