4.5 Population under study

Adults with HIV-1 infection controlled on an outpatient basis in the Infectious Diseases Service of the Hospital Clinic of Barcelona.

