6.2 Design

Although the hypothesis of the study has been based on various congruent information that allow us to face with sufficient guarantee the feasibility of the study and the eventual demonstration of the virological and immunological efficacy of the ATRIPLA® dose reduction strategy, we are not absolutely certain that an unacceptably high virological failure rate (standard viral load ≥ 37 copies/mL on two consecutive occasions) can occur in the arm

experimental. We will consider a priori that the failure of at least 20% (n=6) of the patients in the experimental arm will represent an unacceptably high virological failure rate. In this case, its conclusion will be considered premature. In this extreme case, the data of the patients already included up to the time of the premature conclusion of the study would be analyzed.

The present study is proposed as a proof of concept to be able to formulate another study with a sufficiently large sample size to adequately demonstrate the non-inferiority of the strategy. The results of the present study can help to design the non-inferiority study and to estimate its sample size.

STUDY PROCEDURES

Selection Evaluations								
Clinical Evaluations		Selection						
Informed consent								X
Inclusion and exclusion criteria								X
Assignment of the selection code								X
Vital signs								X
Weight Determination								X
Height determination								X
Demographics								X
Medical history								X
Physical examination								X
Concomitant medications								X
Confirmation of the use of contraceptive methods by the patient and his or her partner								X

Clinical Evaluations	Basal Day 0	S 1 (#)	S 2 (#)	S 4 (#)	S 6 (#)	S 8 (#)	S 12	S 24
Meet Inclusion and Exclusion Criteria	X							
Signed Informed Consent	X							
Vital signs	X							
Weight	X							X
Physical examination	X						X	X
Adverse events		X	X	X	X	X	X	X
Concomitant medications	X	X	X	X	X	X	X	X
Simplified Compliance Questionnaire		X	X	X	X	X	X	X
Test sobre calidad del sueño (Pittsburgh Sleep Quality Index)	X							X
Haematology	X							X
Blood biochemistry	X							X

Clinical Evaluations	Basal Day 0	S 1 (#)	S 2 (#)	S 4 (#)	S 6 (#)	S 8 (#)	S 12	S 24
Standard plasma viral load	X	X	X	X	X	X	X	X
Ultrasensitive plasma viral load (\$)	X							X
HIV-1 reservoir of PBMCs	X							X
Immunology (CD4/CD8)	X						X	X
Immunology Sample	X							X
Pregnancy test (women only) Y(&)	X	X	X	X	X	X	X	X
Pharmacokinetics	X							X

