7.3 Withdrawal criteria (endpoints)

Treatment with the study drug will be terminated **immediately** during the study for any of the following reasons:

- Patient with virologic failure
- Pregnancy during the study.
- Express wish of the patient
- Medical criteria
- Exitus

Treatment with the study drug **may** be terminated during the study for any of the following reasons:

- The medical investigator determines that a SAE is possibly or likely related to the study drug.
- Failure to administer, evaluate, or other study requirements.

8. Treatment of Subjects

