8.1 Treatment Branches

Randomization to two treatment groups: A or B

GROUP A (control): ATRIPLA® at standard daily dose (1 tablet daily) for a period of 24 weeks

GROUP B (experimental): ATRIPLA® at a dose three days per week (1 tablet Monday, Wednesday and Friday) for a period of 24 weeks

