11.1 Sample

The study will be carried out in 60 patients. This is a proof of concept and does not require an ad-hoc sample size calculation.

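### Continuation in the study is stated only after confirmed virologic failure; for other treatment stops the plan is silent, so a patient who stops before confirmation can drop out of the primary endpoint and the n=6 failure count

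*Combined protocol and SAP*

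**What the plan says.** **Reasons for stopping.** Section 6.6 makes ending treatment compulsory for virologic failure, the patient's wish, medical decision, death and pregnancy. It makes it optional for a serious adverse event judged possibly or likely related to the drug, and for non-compliance ("Failure to administer, evaluate, or other study requirements"). Section 7.3 repeats these reasons under a heading that calls them withdrawal criteria.

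**What happens next.** Section 6.6 addresses this once, after a confirmatory result of 37 copies/mL or more: "In this case, unless he or she is against it, the patient would continue in the study". Neither section has an equivalent sentence for the other reasons. The visit tables (sections 6.2 and 17) contain no early-termination visit and no viral load linked to stopping. Section 10.4 follows adverse events up to 30 days after treatment ends, but names no viral load.

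**Design and visits.** Section 1.11 describes an "Open-label, randomized, Phase IV, prospective, pilot, single-center study". The compliance questionnaire and the standard viral load are scheduled at weeks 1, 2, 4, 6, 8, 12 and 24. The first five of these visits are for the experimental arm only.

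**Analysis.** Sections 1.13.1 and 6.1 define the primary endpoint as the proportion below 37 copies/mL at week 24 by intention-to-treat. Section 11.5 rules out imputation and uses available data only. Section 11.7 restricts the analysed population to patients without major deviations.

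**Failure limit.** Section 6.2: "We will consider a priori that the failure of at least 20% (n=6) of the patients in the experimental arm will represent" an unacceptably high failure rate. Failure there means two consecutive values of 37 copies/mL or more.

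**The concern.** An intention-to-treat endpoint at week 24 needs a week-24 outcome for every randomised patient, or a written rule for those without one. The plan secures the measurement expressly for one group of stopped patients and leaves the others to local interpretation. A site that reads section 7.3 literally could treat them as withdrawn and take no further viral load.

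The patients at issue need not resemble the rest. Medical decision has no criteria, non-compliance is left to the investigator, and everyone knows the assigned schedule. Someone who stops because of poor adherence, or after one detectable value but before the repeat test, may be a failure that is never confirmed. There are seven scheduled occasions to detect non-compliance in the experimental arm and two in control, so the opportunity to stop is unequal.

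Two results are at stake: the week-24 suppression proportion, and the count of experimental-arm failures that triggers the plan's own conclusion of an unacceptable rate. The trial is meant to inform a later non-inferiority study, so an optimistic figure would carry forward.

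**Working it through.** **Inputs**
- Total of 60 (section 1.14: "A total of 60 patients will be included"). Section 11.1 gives no calculation ("This is a proof of concept and does not require an ad-hoc sample size calculation").
- Two arms (section 8.1: "Randomization to two treatment groups: A or B"). The allocation ratio is not stated. Equal arms of 30 are inferred from the failure limit.
- Failure limit: at least 20%, n=6 (section 6.2).
- Early-stop rate: not given. The number of failures lost, *k*, is varied from 0 to 4. The share of would-be failures lost, *q*, is varied from 0 to 50%.
- Simplification: the six failures are patients who would be both confirmed failures and unsuppressed at week 24 if they stayed under observation on their assigned schedule.

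**Step 1. The plan's own figure.** 0.20 × 30 = 6, and 6/30 = 20.0%. It is reproduced with 30 in the experimental arm.

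**Step 2. Available-case result when *k* of six failures are lost before confirmation.** Failure = (6 − k)/(30 − k); suppression = 24/(30 − k).

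| k lost | Counted failure | Suppressed | Limit met? |
|---|---|---|---|
| 0 | 6/30 = 20.0% | 24/30 = 80.0% | yes |
| 1 | 5/29 = 17.2% | 24/29 = 82.8% | no |
| 2 | 4/28 = 14.3% | 24/28 = 85.7% | no |
| 3 | 3/27 = 11.1% | 24/27 = 88.9% | no |
| 4 | 2/26 = 7.7% | 24/26 = 92.3% | no |

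One loss takes the arm below the limit whether it is read as a count (5 < 6) or as a percentage. Keeping 30 in the denominator does not change this: 5/30 = 16.7%. If the lost patients were counted as non-response, suppression would stay at 24/30 = 80.0% in every row.

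**Step 3. Chance of reaching six counted failures.** With a true failure rate of 20%, the counted number is taken as binomial with n = 30 and probability 0.20 × (1 − q). P(at least 6) is 57.2% for q = 0, 46.1% for 10%, 34.5% for 20%, 23.6% for 30% and 7.3% for 50%. With a true rate of 30%, it is 92.3% for q = 0 and 76.0% for q = 20%.

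**Step 4. Planned comparison.** Fisher's exact test against a control arm assumed to be 30/30 suppressed gives p = 0.024 for 6/30 failures, 0.024 for 5/29, 0.048 for 4/28 and 0.100 for 3/27. A single loss moves the failure limit but not this p-value; three losses move both.

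**Step 5. Opportunities to detect non-compliance.** Experimental arm: weeks 1, 2, 4, 6, 8, 12 and 24 = 7. Control arm: weeks 12 and 24 = 2.

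**The case against.** The strongest reply is that silence is not a rule. Sections 6.6 and 7.3 speak of ending treatment, not of leaving the study. Viral loads at weeks 12 and 24 are scheduled for both arms and are not limited to patients on treatment. Virologic failure heads the list in section 7.3, yet section 6.6 keeps those patients in the study, so being on that list cannot by itself mean withdrawal. This stands. A reader might infer that only virologic failures are kept and all others leave; the documents do not say so. What they lack is a statement either way for the other reasons.

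A reader might also infer that discretion will be used more often in the experimental arm, or that losses will be informative and unequal. No stopping rate by arm is given, so only the opportunity is shown to be unequal. There is a counterweight: each additional experimental-arm visit also measures viral load, so rebound is more likely to be seen there. Entry requires two years of suppression (section 7.1) and excludes patients whose adherence cannot be ensured (section 7.2). These features reduce the risk. They do not cover a patient who stops between a first detectable value and its repeat.

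Third, a week-24 value after stopping often reflects another regimen. A reader might infer that continued follow-up recovers what would have happened on the assigned schedule. It does not: a patient who re-suppresses on another regimen would count as suppressed. Counting stops as non-response is a legitimate alternative.

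Finally, the bias in the working arises through sections 11.5 and 11.7. That is correct, but changing those sections alone would only choose how to handle a value that nobody was told to collect.

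**Conclusion.** The point holds in conditional form. Continuation is stated only for confirmed virologic failure, no viral load is attached to any other stop, and the analysis sections then permit those patients to vanish from the denominator. Following the plan as written can therefore remove failures from the primary endpoint and from the n=6 count.

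With 30 in the experimental arm and six failures, one loss is enough to miss the 20% limit (17.2%) and raises reported suppression by 2.8 points (82.8% − 80.0%). Three losses raise it by 8.9 points (88.9% − 80.0%). These figures rest on inferred equal allocation, an assumed number of losses and the available-case rule in section 11.5. They show how sensitive the result is and do not predict what will happen. In a proof-of-concept study this is a moderate defect, worth correcting because the remedy is simple.

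**What to change.** In sections 6.6 and 7.3:
- State that stopping study treatment for any reason does not end study follow-up, and separate withdrawal of consent to follow-up as its own category.
- Add a standard viral load at the stopping visit, repeated under the existing confirmation rule if it is 37 copies/mL or more.
- Keep the scheduled week-12 and week-24 viral loads unless consent to follow-up is withdrawn.
- Record the stop date, the reason and the regimen taken afterwards.

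In section 11, label week-24 values obtained after stopping, and show that result beside an analysis counting stops as non-response. Separately, reconcile the intention-to-treat label with sections 11.5 and 11.7 and say how a missing week-24 value counts; the added follow-up does not replace this.

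No stopping rule changes. The cost is protocol wording, one added visit row and one blood sample per stopped patient, plus a repeat where needed. Participants are "Adults with HIV-1 infection controlled on an outpatient basis in the Infectious Diseases Service of the Hospital Clinic of Barcelona" (section 4.5), so obtaining later samples should be feasible. The limitations are that many post-stop week-24 values will describe another regimen, and that the stopping-visit sample detects only rebound already present at that visit.

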6.7 End of rehearsal

The end of the trial will be considered the time of the last visit of the last subject recruited.

7. Subject Selection

7.1 Inclusion criteria for subjects

A patient must meet ALL of the criteria listed below in order to participate:

1. Adults (≥ 18 years)
2. HIV-1 infection, clinical stability, and treatment with ATRIPLA® during the last two years.
3. Standard plasma viral load below the detection limit for at least the last 2 years.
4. CD4 count greater than 350/mm³ at the time of study consideration.

5. Negative pregnancy test in women of childbearing potential, and commitment to use acceptable contraceptive methods from at least 2 weeks before day 1 and until at least 6 months after the last dose of study drug.
6. Patients must have given written informed consent
7. In the opinion of the researcher, to be able to follow the design of the protocol visits.

7.2 Exclusion Criteria

Patients who meet ANY of the following criteria will be excluded from the study:

1. Patients who have had previous virologic failure with any antiretroviral regimen
2. Evidence of prior mutations against efavirenz, tenofovir, or emtricitabine
3. Use of any other chronic treatment besides ATRIPLA that has been introduced in the 6 months prior to the patient's entry into the study
4. Any co-indications to the study drug
5. Any condition that does not allow correct adherence to the study to be ensured at the discretion of the patient's attending physician
6. Uncontrolled pre-existing psychiatric illness
7. Any current signs of alcoholism or other drug use.

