4.1 Investigational Drug Identification

Generic name: efavirenz, emtricitabine, and tenofovir disoproxil (as fumarate). 600 mg/200 mg/245 mg

Trade name: Atripla ®

Composition: Each tablet contains 600 mg efavirenz, 200 mg emtricitabine and 245 mg tenofovir disoproxil (as fumarate).

Pharmaceutical form: film-coated tablet.

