All laboratory specimens should be obtained prior to administration of the first dose of study medication.

(#) These visits will be made only to patients who are in the experimental treatment arm (3-day-per-week treatment)

& At baseline visit it is advised to perform a blood pregnancy test

* Genotypic resistance testing will be performed if the patient has virologic failure (defined by HIV-1 plasma viral load >50 copies/mL confirmed on two consecutive occasions)

Blood biochemistry: lipids (TG, total cholesterol and HDL), creatinine and estimated glomerular filtration rate (CPK-EPI), levels of 25OH vitamin D.

Hematology: Blood count

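### Eligibility does not address hepatitis B: a patient whose hepatitis B is held by the study tablet could be randomised to 3 instead of 7 tablets a week, and the listed blood tests include no liver enzyme

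*Combined protocol and SAP*

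**What the plan says.** **Who enters.** Section 7.1 asks for adults with "HIV-1 infection, clinical stability, and treatment with ATRIPLA® during the last two years", a suppressed viral load for at least two years and a CD4 count above 350/mm³. No hepatitis serology is required.

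**Who is kept out.** Three of the seven exclusions in 7.2 come near the question:
- criterion 2: "Evidence of prior mutations against efavirenz, tenofovir, or emtricitabine"
- criterion 3: "Use of any other chronic treatment besides ATRIPLA that has been introduced in the 6 months prior to the patient's entry into the study"
- criterion 4: "Any co-indications to the study drug"

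The others concern earlier virologic failure, adherence, psychiatric illness, and alcohol or drug use. The selection table (6.2, repeated in section 17) includes medical history but no hepatitis B item.

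**What changes.** Section 4.1 gives the composition: "Each tablet contains 600 mg efavirenz, 200 mg emtricitabine and 245 mg tenofovir disoproxil". Section 8.1 gives the experimental arm: "ATRIPLA® at a dose three days per week (1 tablet Monday, Wednesday and Friday) for a period of 24 weeks". All three drugs are reduced together.

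**What is measured.** The notes to the schedule give "Blood biochemistry: lipids (TG, total cholesterol and HDL), creatinine and estimated glomerular filtration rate (CPK-EPI"), plus 25OH vitamin D. The table marks this panel at baseline and week 24 only. Haematology is a blood count.

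**The concern.** The justification in section 4 argues for wider dose spacing in suppressed HIV. It relies on drug half-lives, efavirenz levels after stopping, a five-days-on study and patient preference. None of this bears on a second infection treated by the same tablet. If tenofovir and emtricitabine also act on hepatitis B, a co-infected patient in the experimental arm would have that treatment reduced as well, without any supporting argument in the plan.

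Patient safety is the main stake. There is also a smaller one for interpretation. Side effects, serious side effects and discontinuations are secondary endpoints (6.1), and a liver event from hepatitis B in one arm of about 30 would count there while saying nothing about the HIV question.

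**Working it through.** The plan states no figure on this point, so there is none to reproduce. The check is mainly of the text.

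**1. Does any existing criterion catch such a patient?** Take someone whose hepatitis B has been held by ATRIPLA for two years or more.
- 7.1, clinical stability and two years on ATRIPLA: met, because the tablet is working.
- 7.2, criteria 1 and 2 (virologic failure, resistance mutations): these concern HIV treatment.
- 7.2, criterion 3 (other chronic treatment): limited to treatment besides ATRIPLA begun in the last 6 months, so it does not apply.
- 7.2, criterion 4: read as contraindications, it refers in effect to a product sheet (Annex I) that is not in the text reviewed. It does not name hepatitis B.
- 7.2, criteria 5 to 7 (adherence, psychiatric illness, substance use): unrelated.

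No criterion in the text excludes this patient.

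**2. Size of the reduction.** Weekly tablets go from 7 to 3: (7 − 3)/7 = 4/7 = 57%, for 24 weeks.

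**3. Would the listed tests show a flare?** The listed tests are lipids, creatinine, estimated GFR, 25OH vitamin D and a blood count. No transaminase, bilirubin or hepatitis B marker is among them. Section 10.1 treats grade IV laboratory alterations as serious, but that rule can act on a liver abnormality only if a liver test is done.

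**4. Chance of enrolling at least one such patient.** The arm size follows from the stopping threshold in 6.2, where 20% equals 6 patients: 6/0.20 = 30. The prevalence p among otherwise eligible patients is not in the documents, so the values below are assumptions. Expected number = 30p. Chance of at least one = 1 − (1 − p)^30.

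| Assumed p | Expected in 30 | (1 − p)^30 | Chance of at least one |
|---|---|---|---|
| 0.5% | 0.15 | 0.860 | 14% |
| 1% | 0.3 | 0.740 | 26% |
| 2% | 0.6 | 0.545 | 45% |
| 3% | 0.9 | 0.401 | 60% |
| 5% | 1.5 | 0.215 | 79% |
| 8% | 2.4 | 0.082 | 92% |

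**5. Pool after an exclusion.** The justification reports more than 1000 patients on effective ATRIPLA, 75% of them for over two years: 0.75 × 1000 = 750. Excluding 0.5% to 8% leaves about 746 to 690. The trial needs 60.

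**The case against.** The strongest objection is that the key premise lies outside the documents. They nowhere say that tenofovir and emtricitabine act on hepatitis B, and they give no flare rate under reduced dosing as opposed to stopping. The justification also cites long intracellular half-lives (39 hours for emtricitabine triphosphate, 150 hours for tenofovir diphosphate). This stands as a limit. The antiviral activity is a general property of the drugs that the sponsor can confirm in its own data sheet, and the half-lives are argued for HIV only. But no flare rate can be given, and a reader who infers that flares would follow and add serious events to the experimental arm goes further than the text allows.

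Three other inferences are tempting but not supported:
- *Criterion 4 could be read in two ways that enrol different patients.* The text is a rough translation, and section 8.2 speaks of contraindicated treatments and points to the technical sheets. A slip for contraindications is by far the likelier explanation. Correcting the word is clerical and does not by itself settle hepatitis B.
- *A flare would be seen only through symptoms.* Section 3.7 refers to routine blood and urine determinations, and section 14 to a pre-treatment blood and urine sample. Neither names a liver test, but detection there is possible. Adverse events are also recorded at weeks 1, 2, 4, 6, 8, 12 and 24 in the experimental arm (weeks 12 and 24 only in the control arm).
- *The site does not know its patients' hepatitis B status.* These are long-term patients of one hospital, and medical history is taken at selection, so the status may well be on file. The gap is that nothing in the plan requires it to be looked up or acted on.

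It can also be said that exclusion is only one possible answer. That is true. It is preferred here because it changes eligibility alone; keeping such patients would call for clinical rules that this review does not propose.

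**Conclusion.** The point holds as a gap in eligibility, compounded by the absence of a liver enzyme from the listed panel. As written, the plan would allow a patient whose hepatitis B is held by ATRIPLA to be randomised to a 57% reduction that its rationale supports only for HIV.

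The chance that this happens to at least one of 30 experimental patients is about 14% to 92% over an assumed prevalence of 0.5% to 8%. The width reflects the absence of any prevalence figure in the documents. A reader might take the upper end as a risk of flare or injury; it is a chance of enrolment only, and the documents offer nothing from which a chance of harm could be computed.

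The conclusion assumes that Annex I confirms the activity of the two drugs against hepatitis B and does not already bar such patients through criterion 4. With those conditions, the change should be made: it protects patients and costs little.

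**What to change.** In 7.2, add chronic hepatitis B (HBsAg positive in the medical record) as an exclusion. Add a matching line to the selection table in 6.2 and section 17, to be checked from existing records. Correct the wording of criterion 4 to the intended term, as a clerical matter.

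The cost is one criterion, one record check per patient and a loss of roughly 4 to 60 of about 750 candidates (750 × 0.005 = 3.75; 750 × 0.08 = 60). At the upper end 690 remain, 11.5 times the 60 required. The results would then apply to patients without chronic hepatitis B, which the report should state. No dose, monitoring or treatment rule is proposed.
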